8.2 Responsibility for Analyses/In-House Blinding

The statistical analysis of the data obtained from this study will be the responsibility of the Clinical Biostatistics department of the Sponsor.

The Sponsor will generate the randomized allocation schedule(s) for study treatment assignment for this protocol, and the randomization will be implemented in IVRS.

This study will be conducted as a double-blind study under in-house blinding procedures. The official, final database will not be unblinded until medical/scientific review has been performed, protocol deviations have been identified, and data have been declared final and complete.

Since the trial is double-blinded, analyses or summaries generated by randomized treatment assignment, and actual treatment received will be limited and documented. In addition, the blinded central imaging vendor will perform the central imaging review without knowledge of treatment group assignment.

The eDMC will serve as the primary reviewer of the unblinded results of the interim analyses and will make recommendations for discontinuation of the study or modification to an executive oversight committee of the Sponsor. An external unblinded statistician and statistical programmer will be responsible for generating unblinded data summaries and presenting them to the eDMC. Depending on the recommendation of the eDMC, the Sponsor may prepare a regulatory submission. If the eDMC recommends modifications to the design of the protocol or discontinuation of the study, this executive oversight committee and limited additional Sponsor personnel may be unblinded to results at the treatment level in order to act on these recommendations. The extent to which individuals are unblinded with respect to results of interim analyses will be documented. Additional logistical details, revisions to the above plan and data monitoring guidance will be provided in the eDMC Charter.

8.3 Hypotheses/Estimation

Objectives and hypotheses of the study are stated in Section 3.0.

8.4 Analysis Endpoints

8.4.1 Efficacy Endpoints

8.4.1.1 Primary

Progression-Free Survival (PFS) – RECIST 1.1 by Blinded Central Imaging Vendor Review

PFS is defined as the time from randomization to the first documented disease progression per RECIST 1.1 based on blinded central imaging vendor review or death due to any cause, whichever occurs first. See Section 8.6.1 for definition of censoring.

Overall Survival (OS)

OS is defined as the time from randomization to death due to any cause. Subjects without documented death at the time of the final analysis will be censored at the date of the last follow-up.

8.4.1.2 Secondary

Objective Response Rate (ORR) – RECIST 1.1 by blinded central imaging vendor review

ORR is defined as the proportion of the subjects in the analysis population who have a CR or PR per RECIST 1.1.

Disease Control Rate (DCR) - RECIST 1.1 by blinded central imaging vendor review

DCR is defined as the proportion of subjects who have achieved CR, PR, or stable disease (SD) after ≥ 5 weeks (the start of the window for the first scheduled scan) based on assessments by the blinded central imaging vendor per RECIST 1.1.

Time to Progression (TTP) - RECIST 1.1 by blinded central imaging vendor review

TTP is defined as the time from randomization to the first documented disease progression per RECIST 1.1. See Section 8.6.1 for definition of censoring.

Duration of Response (DOR) - RECIST 1.1 by blinded central imaging vendor review

For subjects who demonstrate CR or PR, DOR is defined as the time from first documented evidence of CR or PR per RECIST 1.1 until disease progression per RECIST 1.1 or death due to any cause, whichever occurs first. See Section 8.6.1 for definition of censoring.

8.4.2 Safety Endpoints

Safety endpoints are described in Sections 4.2.4.4 and 7.2.

8.5 Analysis Populations

8.5.1 Efficacy Analysis Populations

The Intention-to-Treat (ITT) population will serve as the population for primary efficacy analysis. All randomized subjects will be included in this population. Subjects will be included in the treatment group to which they are randomized.

Details on the approach to handling missing data are provided in Section 8.6 Statistical Methods.

8.5.2 Safety Analysis Populations

The All Subjects as Treated (ASaT) population will be used for the analysis of safety data in this study. The ASaT population consists of all randomized subjects who received at least one dose of study treatment. Subjects will be included in the treatment group corresponding to the study treatment they actually received for the analysis of safety data using the ASaT population. For most subjects this will be the treatment group to which they are randomized. Subjects who take incorrect study treatment for the entire treatment period will be included in the treatment group corresponding to the study treatment actually received. Any subject who receives the incorrect study medication for one cycle but receives the correct treatment for all other cycles will be analyzed according to the correct treatment group and a narrative will be provided for any events that occur during the cycle for which the subject is incorrectly dosed.

At least one laboratory or vital sign measurement obtained subsequent to at least one dose of study treatment is required for inclusion in the analysis of each specific parameter. To assess change from baseline, a baseline measurement is also required.

Details on the approach to handling missing data for safety analyses are provided in Section 8.6 Statistical Methods.

8.6 Statistical Methods

8.6.1 Statistical Methods for Efficacy Analyses

This section describes the statistical methods that address the primary and secondary objectives. Methods related to exploratory objectives will be described in the sSAP.

Efficacy results that will be deemed to be statistically significant after consideration of the Type I error control strategy are described in Section 8.8, Multiplicity. Nominal p-values may be computed for other efficacy analyses, but should be interpreted with caution due to potential issues of multiplicity.

8.6.1.1 Progression-free Survival

The non-parametric Kaplan-Meier method will be used to estimate the PFS curve in each treatment group. The hypotheses of treatment difference in PFS will be tested by the stratified log -rank test. A stratified Cox proportional hazard model with Efron's method of tie handling will be used to estimate the magnitude of the treatment difference (i.e., hazard ratio) between the treatment arms. The hazard ratio and its 95% confidence interval from the stratified Cox model with Efron's method of tie handling and with a single treatment covariate will be reported. The stratification factors used for randomization (see Section 5.4) will be applied to both the stratified log-rank test and the stratified Cox model. Due to the small number in the stratum of presence of macrovascular invasion, subjects from any geographic region or with any level of α -fetoprotein will be combined in this stratum. Thus, the following 5 strata will be used in the stratified log-rank test and the stratified Cox model:

- Macrovascular invasion (No) + Geographic region (Asia without Japan) + α -fetoprotein (ng/mL) (<200)

- Macrovascular invasion (No) + Geographic region (Non-Asia with Japan) + α -fetoprotein (ng/mL) (<200)
- Macrovascular invasion (No) + Geographic region (Asia without Japan) + α -fetoprotein (ng/mL) (\geq 200)
- Macrovascular invasion (No) + Geographic region (Non-Asia with Japan) + α -fetoprotein (ng/mL) (\geq 200)
- Macrovascular invasion (Yes) + Geographic region (Asia without Japan or Non-Asia with Japan) + α -fetoprotein (ng/mL) (<200 or \geq 200)

Since disease progression is assessed periodically, PD can occur any time in the time interval between the last assessment where PD was not documented and the assessment when PD is documented. For the primary analysis, for the subjects who have PD, the true date of disease progression will be approximated by the date of the first assessment at which PD is objectively documented per RECIST 1.1 by blinded central imaging vendor review, regardless of discontinuation of study drug. Sensitivity analyses will be performed for comparison of PFS based on investigator's assessment and PFS analysis for PD per irRECIST by the blinded central imaging vendor review.

In order to evaluate the robustness of the PFS endpoint per RECIST 1.1 by the blinded central imaging vendor review, 2 sensitivity analyses will be performed with a different set of censoring rules. The first sensitivity analysis is the same as the primary analysis except that (1) the date of documented PD or death will be the progression date, regardless of whether or not new anti-cancer treatment is initiated and (2) it censors at the last disease assessment, regardless of whether or not new anti-cancer treatment is initiated if no PD and no death occur. The second sensitivity analysis is the same as the first sensitivity analysis, except that it considers discontinuation of treatment due to reasons other than complete response or initiation of an anti-cancer treatment subsequent to discontinuation of study-specified treatment, whichever occurs later, to be a PD event for subjects without documented PD or death. The censoring rules for primary and sensitivity analyses are summarized in [Table 8](#).

Table 8 Censoring Rules for Primary and Sensitivity Analyses of PFS

| Situation | Primary Analysis | Sensitivity Analysis 1 | Sensitivity Analysis 2 |
|---|---|--|---|
| PD or death documented after ≤ 1 missed disease assessment, and before new anti-cancer therapy, if any | Progressed at date of documented PD or death | Progressed at date of documented PD or death | Progressed at date of documented PD or death |
| PD or death documented after ≥ 2 consecutive missed disease assessments or after new anti-cancer therapy | Censored at last disease assessment prior to the earlier date of ≥ 2 consecutive missed disease assessment and new anti-cancer therapy, if any | Progressed at date of documented PD or death | Progressed at date of documented PD or death |
| No PD and no death; and new anti-cancer therapy is not initiated | Censored at last disease assessment | Censored at last disease assessment | Progressed at treatment discontinuation due to reasons other than complete response; otherwise censored at last disease assessment if still on study or completed study therapy |
| No PD and no death; new anti-cancer therapy is initiated | Censored at last disease assessment before new anti-cancer therapy | Censored at last disease assessment | Progressed at date of new anti-cancer therapy |

The proportional hazards assumption on PFS will be examined using both graphical and analytical methods if warranted. The log [-log] of the survival function vs. time for PFS will be plotted for the comparison between pembrolizumab and the control arm. If the curves are not parallel, indicating that hazards are not proportional, supportive analyses may be conducted to account for the possible non-proportional hazards effect associated with immunotherapies: for example, using Restricted Mean Survival Time method [51], parametric method [52], etc. Further details of sensitivity analyses will be described in supplemental SAP.

The main PFS analysis will be conducted according to the hypotheses testing plan as described in Section 8.7 Interim Analyses and Section 8.8 Multiplicity. The supportive analysis of the PFS data available at the time of the final OS analysis will be also conducted.

8.6.1.2 Overall Survival

The non-parametric Kaplan-Meier method will be used to estimate the survival curves. The hypotheses of treatment difference in survival will be tested by the stratified log -rank test. A stratified Cox proportional hazard model with Efron's method of tie handling will be used to estimate the magnitude of the treatment difference (i.e., the hazard ratio). The hazard ratio and its 95% confidence interval from the stratified Cox model with a single treatment covariate will be reported. The stratification factors used for randomization will be applied to both the stratified log-rank test and the stratified Cox model. The same 5 strata defined for the PFS analysis (see Section 8.6.1.1) will be used for the OS analysis.

Subjects in the control arm are expected to discontinue treatment earlier compared to subjects in the pembrolizumab arm, and may switch to another anti PD-1 treatment following the verification of progressive disease by blinded central imaging vendor review. Exploratory analyses to adjust for the effect of treatment switching to other PD-1 therapies on OS may be performed based on recognized methods, e.g. the Rank Preserving Structural Failure Time model proposed by Robins and Tsiatis [53], two-stage model, etc., based on an examination of the appropriateness of the data to the assumptions required by the methods.

8.6.1.3 Objective Response Rate

Stratified Miettinen and Nurminen's method [49] with weights proportional to the stratum size will be used for comparison of the objective response rates between the treatment arms. A 95% confidence interval for the difference in response rates between the pembrolizumab arm and the control arm will be provided. The stratification factors used for randomization will be applied to the analysis. The same 5 strata defined for the PFS analysis (see Section 8.6.1.1) will be used for the ORR analysis.

The ORR analysis will be conducted according to the hypotheses testing plan as described in Section 8.7 Interim Analyses and Section 8.8 Multiplicity.

8.6.1.4 Disease Control Rate

Stratified Miettinen and Nurminen's method [49] with weights proportional to the stratum size will be used for comparison of the DCR between the treatment arms. A 95% confidence interval for the difference in response rates between the pembrolizumab arm and the control arm will be provided. The stratification factors used for randomization will be applied to the analysis. The same 5 strata defined for the PFS analysis (see Section 8.6.1.1) will be used for the DCR analysis.

8.6.1.5 Time to Progression

The non-parametric Kaplan-Meier method will be used to estimate the TTP curve in each treatment group. A stratified Cox proportional hazard model with Efron's method of tie handling will be used to estimate the magnitude of the treatment difference (i.e., hazard ratio) between the treatment arms. The hazard ratio and its 95% confidence interval from the stratified Cox model with Efron's method of tie handling and with a single treatment covariate will be reported. The stratification factors used for randomization (see Section 5.4) will be applied to both the stratified log-rank test and the stratified Cox model. The same 5 strata defined for the PFS analysis (see Section 8.6.1.1) will be used for the TTP analysis.

Since disease progression is assessed periodically, progressive disease (PD) can occur any time in the time interval between the last assessment where PD was not documented and the assessment when PD is documented. For the analysis, for the subjects who have PD, the true date of disease progression will be approximated by the date of the first assessment at which PD is objectively documented per RECIST 1.1 by blinded central imaging vendor review, regardless of discontinuation of study drug. Unlike in PFS analysis, death is not considered as an event. Censoring rules for TTP are summarized in [Table 9](#).

Table 9 Censoring Rules for TTP

| Situation | Primary Analysis |
|---|--|
| Death only | Censored at date of randomization or date of last non-PD disease assessment, whichever is later |
| No PD and no death; new anticancer treatment is not initiated | Censored at last non-PD disease assessment |
| No PD and no death; new anticancer treatment is initiated | Censored at last non-PD disease assessment before new anticancer treatment |
| PD documented after ≤ 1 missed disease assessment | Progressed at date of documented PD |
| PD documented after ≥ 2 missed disease assessments | Censored at last disease assessment prior to the ≥ 2 consecutive missed disease assessments |

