4.2.4.1.2 Secondary Efficacy Endpoint

The secondary efficacy objectives of this study are to:

- (1) Compare ORR per RECIST 1.1 assessed by a blinded central imaging vendor.
- (2) Evaluate DOR, DCR and TTP per RECIST 1.1 assessed by a blinded central imaging vendor.

Measurable disease will be confirmed centrally at enrollment, prior to subject randomization, to ensure that the assessment of measurable disease is accurate. These endpoints have been chosen as ancillary markers of efficacy in a population with few treatment options.

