8.8 Multiplicity

The multiplicity strategy specified in this section will be applied to the two primary hypotheses (superiority of pembrolizumab on PFS or OS) and the secondary hypothesis of superiority of pembrolizumab in ORR.

The overall Type I error across the testing of the OS, PFS, and ORR hypotheses is strongly controlled at $\alpha=2.5\%$ (one-sided). The multiplicity strategy will follow the graphical approach of Maurer and Bretz [50]. [Figure 3](#) provides the multiplicity strategy diagram of the study.

[figure not shown]

Figure 3 Multiplicity Strategy

In the diagram shown in [Figure 3](#), when a particular null hypothesis is rejected, the arrows leading to it are removed, and the Type I error allocated to the null hypothesis that was rejected is re-distributed to the other two hypotheses. The arrows on the diagram show how the Type I error allocated to a hypothesis that was successfully tested will be re-distributed for the testing of the other two hypotheses. Initially, $\alpha=2.3\%$ ($23/25$ of the overall total $\alpha=2.5\%$ for testing the OS, PFS, and ORR) is allocated to the OS hypothesis and $\alpha=0.2\%$ is allocated to the PFS hypothesis.

The testing of the PFS, OS, and ORR will proceed as follows.

PFS Hypothesis: The testing of the primary PFS hypothesis will be conducted at the time of the first OS IA. The testing of the PFS hypothesis will be based on a PFS test statistic calculated only from study data available at the time of the main PFS analysis at the first OS IA. The PFS hypothesis will initially be tested at Type I error $\alpha=0.2\%$. Depending on the result of the initial testing of the PFS hypothesis and the results of testing of the OS and ORR hypotheses, the PFS hypothesis can be tested at Type I error levels of $\alpha=0.2\%$, $=1.35\%$, or $=2.5\%$. [Table 13](#) shows the boundary thresholds corresponding to a successful testing of the PFS hypothesis at each of these Type I error levels. From [Table 13](#), to declare success on the PFS hypothesis at Type I error $\alpha=0.2\%$, the nominal calculated p-value should be ≤ 0.002 , and the PFS hazard ratio should be ≤ 0.71 . At the time of the main PFS analysis at approximately Month 22, it is expected that 331 PFS events would have been accumulated under assumptions specified in Section 8.9 - Sample Size and Power Calculations.

Table 13 Efficacy Boundaries for Testing the PFS Hypothesis

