8.9 Sample Size and Power Calculations

The study will randomize subjects in a 2:1 ratio into pembrolizumab arm and the control arm. Approximately 408 subjects are required to be enrolled in order to test the OS hypothesis at the desired study requirements.

The analysis of the OS endpoint is event driven. The testing of the OS hypothesis is conducted upon accumulating a preset number of events. The study is designed and will be conducted to accumulate approximately 273 OS events.

PFS Analysis: As described in Section 8.7 Interim Analysis, the main PFS analysis will be conducted at the same time as the first OS IA at approximately Month 22 of the study. It is projected that approximately 331 PFS events will be accumulated at this time. With 331 PFS events, the testing of the PFS hypothesis at Type I error $\alpha=0.2\%$ has 94% power to demonstrate that pembrolizumab is superior to the control with respect to PFS if the underlying PFS hazard ratio (pembrolizumab/control) is 0.60.

The power calculation is based on the following assumptions: 1) PFS follows an exponential distribution with a median of 2.5 months in the control arm; 2) An enrollment period of 16 months; 3) a minimum follow-up of approximately 6 months; and 4) A yearly drop-out rate of $\sim 10\%$.

OS Analysis: A total of 273 OS events are required to test the OS hypothesis at Type I error $\alpha=2.3\%$ with $\sim 92\%$ power (see [Table 14](#)) if the underlying OS hazard ratio (pembrolizumab/control) is 0.65. A total of 408 subjects are needed to be enrolled into the study in order to accumulate 273 OS events at approximately Month 35 of the study.

The sample size and power calculation is based on the following assumptions: 1) OS follows a piece-wise exponential distribution with zero hazard during the first month and a median of 10 months in the control arm; 2) An enrollment period of 16 months; 3) a minimum follow-up of 19 months; and 4) A yearly dropout rate of $\sim 2\%$.

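### The TTP curve censors deaths without progression, so one minus Kaplan-Meier overstates the proportion with documented progression in each arm; a cumulative incidence curve should be added

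*Combined protocol and SAP*

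**What the plan says.** Section 8.4.1.2 gives the definition: "TTP is defined as the time from randomization to the first documented disease progression per RECIST 1.1". Section 8.6.1.5 sets out the analysis:

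- Curve: "The non-parametric Kaplan-Meier method will be used to estimate the TTP curve in each treatment group".
- Deaths: "Unlike in PFS analysis, death is not considered as an event". In Table 9 the row for death only reads "Censored at date of randomization or date of last non-PD disease assessment, whichever is later".
- Treatment comparison: a stratified Cox model "will be used to estimate the magnitude of the treatment difference (i.e., hazard ratio) between the treatment arms".

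No cumulative incidence function or other competing-risk analysis of TTP appears anywhere in the documents. Section 8.6.1 leaves only the methods for exploratory objectives to the supplemental SAP, so the method for TTP, a secondary endpoint, should be found here.

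The role of TTP is descriptive. Section 4.2.4.1.2 lists the objective as "Evaluate DOR, DCR and TTP per RECIST 1.1 assessed by a blinded central imaging vendor", and section 3.2 attaches no hypothesis to it. Section 8.8 covers other endpoints: "The overall Type I error across the testing of the OS, PFS, and ORR hypotheses is strongly controlled". Table 11 does not list TTP. Section 8.6.1.6 has it analysed at the interim and final OS analyses.

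**The concern.** A subject who dies without PD cannot later have documented PD. Kaplan-Meier treats that subject, once censored, as still able to progress at the rate of those who remain under observation. One minus the curve therefore estimates a progression probability in a hypothetical population without deaths. It does not estimate the proportion of randomized subjects with documented progression, which is how readers usually take a TTP curve and the rates read from it.

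Deaths before documented PD are plausible here. Section 4.1 says most HCC arises in cirrhosis. Section 8.9 assumes a control median OS of 10 months. Section 7.1.4.1.3 images subjects who stop treatment without PD only every 12 weeks, which leaves time to die before PD is seen. At stake is the accuracy, within each arm, of a descriptive secondary result.

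**Working it through.** **1. Inputs.** From section 8.9: "PFS follows an exponential distribution with a median of 2.5 months in the control arm", and a PFS hazard ratio of 0.60. The PFS hazards per month are

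- control: ln 2 / 2.5 = 0.277
- pembrolizumab: 0.60 × 0.277 = 0.166

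The share f of PFS events that are deaths without PD is not in the documents. It is assumed, over 5% to 30%, and first taken as equal in both arms.

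**2. Check of the PFS inputs.** The plan states no TTP figure. Its PFS power can be reproduced with 331 events, 2:1 allocation and one-sided alpha 0.2%:

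√(331 × 2/3 × 1/3) × |ln 0.60| − 2.878 = 8.577 × 0.511 − 2.878 = 1.50, which gives power 93.4%.

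Sections 8.1 and 8.9 state 94%, so the inputs agree. (Table 13 prints 99.00% for the same test; that is a separate matter and does not affect TTP.)

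**3. Formulas**, with constant hazards and total PFS hazard h:

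- one minus Kaplan-Meier, deaths censored: 1 − exp(−(1−f)·h·t)
- cumulative incidence of PD: (1−f)·(1 − exp(−h·t))

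Example: control, f = 0.10, t = 6 months. Here h·t = 1.664. Kaplan-Meier gives 1 − exp(−1.497) = 77.6%. Cumulative incidence gives 0.90 × (1 − 0.189) = 72.9%.

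**4. Results at 6 months** (%; excess in points):

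| f | Control 1−KM | Control CIF | Excess | Pembro 1−KM | Pembro CIF | Excess |
|---|---|---|---|---|---|---|
| 5% | 79.4 | 77.0 | 2.4 | 61.3 | 60.0 | 1.3 |
| 10% | 77.6 | 72.9 | 4.7 | 59.3 | 56.8 | 2.5 |
| 15% | 75.7 | 68.9 | 6.8 | 57.2 | 53.7 | 3.5 |
| 20% | 73.6 | 64.8 | 8.8 | 55.0 | 50.5 | 4.5 |
| 30% | 68.8 | 56.7 | 12.1 | 50.3 | 44.2 | 6.1 |

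**5. Plausible range of f.** Section 8.9 assumes no deaths in month 1 and a control median OS of 10 months, so the death hazard afterwards is ln 2 / 9 = 0.077. If progression-free subjects died at that full rate, the control share would be 0.077/0.277 = 28%. Allowing for the death-free first month, it is exp(−0.277) × 0.278 = 0.758 × 0.278 = 21%. It is lower if death is rarer before progression than after. So 10% to 20% is a reasonable working range, with 20% near the top.

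**6. The planned Cox hazard ratio.** This was simulated with 408 subjects, 2:1 allocation, scans every 6 weeks, deaths censored by Table 9, Efron ties, no strata, independent progression and death times, 200 replicates and a true PD hazard ratio of 0.60:

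| Hazard ratio for death without PD | Deaths censored | No deaths |
|---|---|---|
| 0.3 | 0.606 | 0.606 |
| 0.6 | 0.600 | 0.599 |
| 1.0 | 0.593 | 0.595 |

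Censoring deaths leaves the estimate essentially unchanged.

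**7. Difference between the curves** (control minus pembrolizumab, points):

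| Assumption about deaths without PD | Month | From KM | From CIF |
|---|---|---|---|
| Share 10% in both arms | 6 | 18.3 | 16.1 |
| Share 20% in both arms | 6 | 18.6 | 14.3 |
| Equal hazard in both arms, control share 10%, PFS HR 0.60 | 6 | 21.2 | 20.3 |
| Same | 12 | 13.9 | 14.8 |
| Same | 18 | 7.1 | 10.2 |
| Control share 20%, PD HR 0.60, death HR 1.5 | 6 | 18.6 | 20.1 |
| Same | 12 | 13.3 | 20.2 |

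The excess within each arm always has the same sign. The distortion of the difference does not.

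**The case against.** The case against acting has four parts.

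- **The estimator is coherent.** Censoring deaths fits the plan's TTP definition and describes the cause-specific hazard of PD. Section 8.6.1.5 does not present one minus the curve as a progression probability and names no landmark times for TTP. Estimates at specific time points are promised for DOR, and the Kaplan-Meier event rates in the section 8.1 summary follow the sentences on PFS and OS.
- **The size is assumed.** The share of deaths without PD is not in the documents, and 20% is near the ceiling from the plan's own OS assumption. Eligibility (Child-Pugh A, ECOG 0 or 1, life expectancy over 3 months) selects against early death.
- **No decision depends on it.** TTP has no hypothesis and no alpha, and PFS already counts deaths as events.
- **Replacing Kaplan-Meier would cost comparability** with earlier trials.

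All four limit the size, the severity or the remedy, and they stand to that extent. None makes one minus Kaplan-Meier equal to the proportion with documented progression once a subject has died without PD, and a published TTP curve and its median invite that reading.

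**Conclusion.** The point holds within each arm. Kaplan-Meier with deaths censored overstates the proportion with documented progression, by about 5 to 9 points on control and 2.5 to 4.5 points on pembrolizumab at 6 months. Those figures rest on constant hazards, the plan's PFS inputs and an assumed 10% to 20% death share, the same in both arms. The direction needs only that some subjects die before PD; the size depends on the assumption.

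A reader might go further and infer that the plan exaggerates the treatment difference in TTP. The documents do not support that. The planned comparison is the Cox hazard ratio, which step 6 shows to be essentially unaffected. For a difference read off the curves, the sign depends on the hazard of death without PD in each arm. Taking the same share in both arms amounts to a hazard ratio of 0.60 for such deaths, and that choice produces the apparent overstatement. Equal death hazards reverse it by month 12, and a higher death hazard on pembrolizumab reverses it by month 6. The plan's OS hazard ratio of 0.65 concerns all deaths, including those after progression, so it does not settle the matter.

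Severity is low: this is a worthwhile improvement to a descriptive secondary analysis and does not touch the trial's primary conclusions.

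**What to change.** In section 8.6.1.5:

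1. Add the Aalen-Johansen cumulative incidence of PD by arm, with death without PD as the competing event and 95% confidence intervals at fixed times (for example 6 and 12 months), and name it as the estimate of progression probability.
2. Keep the Kaplan-Meier curve, stating that deaths are censored and that it is shown for comparison with other trials.
3. Label the stratified Cox result a cause-specific hazard ratio for PD.
4. State which deaths count as competing events, and from what date. One workable choice is the deaths that Table 8 counts as events in the primary PFS analysis, dated at death.

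No new data are needed, since PD and death dates are already collected for PFS and OS. The cost is a few lines of SAP text, a standard procedure, and two TTP displays to explain instead of one.
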